Within subjects paired t-tests will be used to assess significance of change in the different Scales used.

Sample Size Calculation

A number of 15 study subjects was selected to guarantee recruitment. This is a pilot feasibility study to evaluate for common side effects. The study will support the development of future larger clinical trials. The study design is not powered to detect significant effects, but rather to determine feasibility of administering Austedo for 6 weeks in this population.

Planned Number of Sites: One (1). Parkinson's Disease and Movement Disorders Center at the University of Pennsylvania. Philadelphia, PA.

Number of Subjects: 15

Study Duration per Subject/Visit Schedule: Thirteen (13) weeks, or less, if unable to titrate up to 48 mg/day of AUSTEDO.

Expected rate of enrollment (subjects/month): Two (2).

Study Start/FPFV: 02/01/2018; Study End/LPLV: 12/31/2018; Final Report: 05/31/2019

Publication Plan:

Once the data is analyzed, manuscript submission is planned in a scientific journal relevant to the field of movement disorders. The following is a list of journals in descending order of preference:

- 1. Movement Disorders (Wiley).
- 2. Parkinsonism & related disorders (Elsevier).
- 3. Tremor and other hyperkinetic movements (Columbia University Libraries).

TABLE OF CONTENTS

	TITLE PAGE	1
	Table 1: ABBREVIATIONS AND DEFINITIONS	2
	SYNOPSIS	4
	TABLE OF CONTENTS	7
1.	INTRODUCTION	11
1.1	Overview of dystonia and its treatments	11
1.2	Background	11
1.2.1	Overview on AUSTEDO	11
1.2.2	Clinical studies with AUSTEDO	12
1.3	Study Rationale	13
1.3.1	Selection of AUSTEDO Dose and Schedule of Administration	14
2.	TRIAL OBJECTIVES	15
2.1	Primary Objective	15
2.2	Secondary Objectives	15
2.3	Safety Outcome Assessments	15
2.4	Efficacy Outcome Assessments	16
3.	STUDY METHODS	17
3.1	Study Design	17
3.2	Site	17
3.3	Number of Subjects	17
3.4	Study Population	18
3.4.1	Inclusion Criteria	18
3.4.2	Exclusion Criteria	18
3.4.3	Duration of Subject Participation	19
3.4.4	Estimated Study Duration	20
3.5	Study Visit and Assessment Schedule	20
3.5.1	Schedule for subjects able to increase to and maintain maximum AUSTEDO dose	20
3.5.1.1	Visit 1: Screening (Week 1)	20
3.5.1.2	Visit 2: Ramp-up period (Week 2 +/- 2 Days)	20

3.5.1.3	Visit 3: Maintenance dose starts	21
3.5.1.4	Visit 4: Maintenance dose ends	21
3.5.1.5	Visit 5: Post treatment evaluation	22
3.5.2	Special situations that could cause changes in Study Visit Schedule	22

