1. INTRODUCTION

1.1 Overview of dystonia and its treatments

Dystonia is defined as a movement disorder characterized by sustained or intermittent muscle contractions causing abnormal, often repetitive, movements, postures, or both. Dystonic movements are typically patterned and twisting, and may be tremulous. Dystonia is often initiated or worsened by voluntary action and associated with overflow muscle activation. Dystonia is classified along two axes: clinical characteristics, including age at onset, body distribution, temporal pattern and associated features (additional movement disorders or neurological features); and etiology, which includes nervous system pathology and inheritance. The clinical characteristics fall into several specific dystonia syndromes that help to guide diagnosis and treatment.¹

Whenever a cause for the dystonia is identified, it opens the door to specific, etiology-based treatments. However, in the majority of cases, a cause cannot be recognized, and treatments are based on symptoms. Treatment options include counseling and education, oral medications, botulinum toxin injections, and several surgical procedures.² Of note, none of the oral medications commonly used to treat dystonia has been subject to large-Scale, double-blinded, placebo-controlled trials, and there is no FDA-approved oral medication for treatment of dystonia. Much of the evidence supporting their use comes from small controlled trials, non-blinded trials, retrospective reviews, and anecdotal experience.²

Different classes of medications are often used to treat dystonia.² These include:

- Anticholinergics: These drugs are thought to work by blocking muscarinic acetylcholine receptors in the basal ganglia. Examples include trihexyphenidyl, benztropine, biperidin, ethopropazine, orphenadrine and procyclidine.
- Benzodiazepines: Benzodiazepines amplify transmission through GABA receptors. Commonly
 used benzodiazepines include alprazolam, chlordiazepoxide, clonazepam, and diazepam.
- Dopaminergics: Augmenting dopamine transmission with levodopa is dramatically effective in dopa-responsive dystonia, which is most often caused by mutations in the GCH1 gene encoding the enzyme GTP-cyclohydrolase.
- Dopamine depleters: Tetrabenazine, a reversible vesicular monoamine transporter 2 (VMAT2) inhibitor for oral administration, may be useful for some subjects with dystonia, particularly those with tardive dystonia.

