Adverse events will be monitored throughout the study and will be reported after drug initiation. Dose reductions, suspensions, and withdrawals due to adverse events will be recorded. ECG readings, the Columbia Suicide Severity Rating Scale and the Stanford Sleepiness Scale will be assessed at all scheduled study Visits. The Mini Mental (MMSE) Scale will be performed at screening and at the final on-treatment Visit (Visit 4, usually during week 12). A video examination of the study subjects will be made at screening (right before initiation of the study drug), and after 6 weeks on AUSTEDO at a steady dose (right before drug cessation). Part III of the MDS-UPDRS will be performed at both of these Visits as well to screen for the appearance of drug-induced parkinsonism. Videos will be sent to raters blinded to Visit number and recording date, who will assess changes in the subjects' dystonic symptoms. Patients will be contacted on a weekly basis via telephone during the ramp-up.

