3.6.1.8 MDS-UPDRS (Part III)

To screen for the development of drug-induced parkinsonism, a possible side effect of AUSTEDO use, the MDS-UPDRS (Part III)²⁰ will be administered during Visits 1, 4 and during the early termination Visit, if such a Visit happens. It will remain at the investigator's discretion to either discontinue the study drug, or to reduce the dose to a new, maximum, well-tolerated dose if clinically-significant, new-onset drug-induced parkinsonism is identified at any point during the course of the trial, even if detected during Visits during which the MDS-UPDRS (Part III) is not administered. Figure 7 shown below shows this Scale embedded in a data capture form:

Figure 7

Date: DD – MMM – YYYYY Study subject number: ____

Visit Number (circle one): 1 4 Early termination Visit

The AUDYT Trial MDS-UPDRS (Part III)

3.1	Speech	
3.2	Facial expression	
3.3a	Rigidity- Neck	
3.3b	Rigidity- RUE	
3.3c	Rigidity- LUE	
3.3d	Rigidity- RLE	
3.3e	Rigidity- LLE	
3.4a	Finger tapping- Right hand	
3.4b	Finger tapping- Left hand	
3.5a	Hand movements- Right hand	
3.5b	Hand movements- Left hand	
3.6a	Pronation- supination movements- Right hand	
3.6b	Pronation- supination movements- Left hand	
3.7a	Toe tapping-Right foot	
3.7b	Toe tapping- Left foot	
3.8a	Leg agility- Right leg	
3.8b	Leg agility- Left leg	

3.9	Arising from chair			
3.10	Gait			
3.11	Freezing of gait			
3.12	Postural stability			
3.13	Posture			
3.14	Global spontaneity of movement			
3.15a	Postural tremor- Right hand			
3.15b	Postural tremor– Left hand			
3.16a	Kinetic tremor– Right hand			
3.16b	Kinetic tremor- Left hand			
3.17a	Rest tremor amplitude- RUE			
3.17b	Rest tremor amplitude- LUE			
3.17c	Rest tremor amplitude- RLE			
3.17d	Rest tremor amplitude- LLE			
3.17e	Rest tremor amplitude- Lip/jaw			
3.18	Constancy of rest			
	Were dyskinesias presen	□ No □ Yes		
	Did these movements interfere with ratings?	□ No □ Yes		

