3.7.1.2 Secondary Safety Endpoints

Safety will be assessed by the documentation of all adverse events throughout the study. Serious adverse events will be reported, as appropriate. Twelve lead ECG will be performed during all scheduled study Visits (including an early termination Visit, if one happens) to screen for prolongation of the QT interval. In addition, the following Scales will be assessed:

- 1. Columbia Suicide Severity Rating Scale.
- 2. Stanford Sleepiness Scale.
- 3. Mini Mental Scale.
- 4. MDS-Unified Parkinson's Disease Rating Scale.
- 3.7.2 Efficacy Endpoints

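### With 15 subjects, a paired t-test on MDS-UPDRS Part III cannot show parkinsonism confined to three or fewer, so the scale needs a subject-level summary

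*Combined protocol and SAP*

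**What the plan says.** Section 3.1 gives the purpose of the scale: "Part III of the MDS-UPDRS will be performed at both of these Visits as well to screen for the appearance of drug-induced parkinsonism". Sections 2.3 and 3.6.1.8 place it at Visits 1 and 4 and at any early termination visit. Section 3.7.1.2 lists "MDS-Unified Parkinson's Disease Rating Scale" among the secondary safety endpoints, with no summary measure, threshold or case definition.

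The Synopsis, under Statistical Methods, has a single sentence: "Within subjects paired t-tests will be used to assess significance of change in the different Scales used". The Synopsis also lists MDS-UPDRS among the safety scales, so the sentence covers it as written. Section 3.7.2.2 names the paired t-test for the GDS only. Section 6.1.1 defines the safety population and says that safety data will be summarized, but not how this scale will be.

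On size, the Synopsis says "A number of 15 study subjects was selected to guarantee recruitment" and "The study design is not powered to detect significant effects". No significance level or sidedness is given.

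**The concern.** The scale is a screen for an effect that may appear in a few subjects, but the only analysis stated for it is a test of the group mean. When a few subjects worsen and the rest do not, each affected subject raises the standard deviation along with the mean, so the t statistic stays low.

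Section 1.3 names parkinsonism as one of three side effects that limit use of the parent drug, and the trial's primary objective is safety and tolerability. A report that Part III did not change significantly could be taken as reassurance when two or three of 15 subjects had developed parkinsonism. That reading is realistic: section 1.2.2 summarises an earlier tardive dyskinesia trial by saying that parkinsonism on the UPDRS motor subscale did not worsen in either group.

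There is a second, less certain mechanism. Section 1.1 says of dystonia: "Dystonic movements are typically patterned and twisting, and may be tremulous". The Part III form scores items such as "Postural tremor- Right hand", along with speech, gait and posture. If some of these items reflect dystonia, improvement in dystonia could offset a rise caused by parkinsonism.

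**Working it through.** The plan has no power calculation for this scale, so there is no figure to reproduce.

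**Inputs.** n = 15 (Synopsis and section 3.3). The test is the paired t-test (Synopsis). Two-sided 0.05 is an assumption. The size of the rise, the SD of change and the rate of parkinsonism are not in the documents; step 1 needs none of them.

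**Step 1: exact bound.** Let k of n subjects rise and let no other subject's score rise. With changes x, the sum of x is at most the sum over the k risers, so by Cauchy-Schwarz (Σx)² ≤ k·Σx² whenever the mean change is positive. Putting this into t = mean/(SD/√n) gives

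t_max = √[k(n−1)/(n−k)].

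For n = 15 the critical value is t(0.975, 14) = 2.145.

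| Subjects affected | t_max | Smallest two-sided p |
|---|---|---|
| 1 | √(14/14) = 1.00 | 0.33 |
| 2 | √(28/13) = 1.47 | 0.16 |
| 3 | √(42/12) = 1.87 | 0.082 |
| 4 | √(56/11) = 2.26 | 0.041 |

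Up to three affected subjects (20%) cannot give a significant result, whatever the rise. Withdrawn subjects are not replaced (section 3.5.2.5), so n may be smaller; the limit of three also holds for n = 10 to 14 (at n = 10, t_max = 1.96 against 2.262). With a one-sided 0.05 test, three affected could just reach significance (p = 0.041) but two could not (p = 0.082).

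**Step 2: random change in everyone.** The bound no longer applies exactly once unaffected scores can also rise. Simulation of 100,000 trials per setting, assuming SD 2, 3 or 5 points and a rise of 5, 10 or 15 points in affected subjects, gives these chances of significant worsening:

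| Subjects affected | Chance |
|---|---|
| 1 | 1 to 5% |
| 2 | 3 to 9% |
| 3 | 8 to 18% |
| 4 | 12 to 53% |
| 5 | 17 to 91% |

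**Step 3: offset by dystonia.** This is illustrative only, since the documents give no size. If three subjects rise 10 points and twelve fall 2.5, the mean change is (30 − 30)/15 = 0 and p = 1.0.

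**Step 4: a subject-level count.** Exact (Clopper-Pearson) 95% intervals: 0/15, 0 to 21.8%; 1/15, 0.2 to 31.9%; 2/15, 1.7 to 40.5%; 3/15, 4.3 to 48.1%. The chance that at least one of 15 subjects is affected is 1 − (1 − p)^15: 53.7% at a true rate of 5%, 79.4% at 10% and 96.5% at 20%.

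**Step 5: why the count needs a threshold.** The rigidity (5), bradykinesia (10 + 1), facial expression (1) and rest tremor (5 + 1) items number 23. If each worsened by chance in 2 to 5% of unaffected subjects, independently (assumed), a rule of any worsening on any item would flag 1 − 0.98^23 = 37% to 1 − 0.95^23 = 69% of them.

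**The case against.** A reader might infer that parkinsonism is to be judged by this t-test alone. The documents do not support that. Sections 2.3 and 3.6.1.8 provide for the investigator to identify clinically significant parkinsonism at any point, including visits without the scale. All adverse events are recorded with severity and causality, and section 3.7.1.1 records why subjects fail to reach or keep the maximal dose. Two or three recognised cases could therefore appear in the report whatever the p-value. The plan also says openly that it is not powered for significance.

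The t-test premise is one general Synopsis sentence that cannot be literal for every scale: the PGI-I has no baseline value and is summarized by its median (section 3.7.2.1). Section 3.7.2.2 may show the real intent, with the test meant for the GDS only.

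These points stand, and they limit the concern without removing it. If the Synopsis sentence does not govern, no analysis of Part III is stated at all. Lack of power is a reason to keep a p-value off a harm outcome. The other routes also have gaps:

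- The neurologic examination is at the first and final visits (section 3.6.1.3). The final visit is at least a week after stopping, and section 4.1.4 gives a metabolite half-life of 9 to 10 hours, so it is about 17 half-lives or more off drug (168/10 = 16.8).
- The video raters are told to score dystonia only.
- Adverse events are elicited by a nonspecific question, and section 5.1.1 generally excludes signs of the disease under study, although worsening of baseline symptoms is included.
- Section 5.1.1.2 provides for dose reduction when parkinsonism develops, so an affected subject's Visit 4 score may reflect a lower dose.

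For completers, Visit 4 Part III is thus the only scheduled structured assessment of parkinsonism on drug.

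**Conclusion.** The concern holds in a limited form. If the Synopsis sentence applies to Part III, the test cannot reach two-sided 0.05 when three or fewer of 15 subjects rise and the others do not. This is exact and needs no assumed SD or effect size; it rests only on the two-sided 5% level. With random change in all subjects, the chance of detecting three affected is 8 to 18% under the assumed ranges. A non-significant mean change therefore does not show that parkinsonism is absent.

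A reader might go further and conclude that improving dystonia will cancel parkinsonism in the total score. The overlap is plausible from the item list, but the documents do not say that dystonia moves this score and give nothing from which to compute by how much. It remains a possible further source of masking, of unknown size.

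The Synopsis and section 3.7.2.2 need to be reconciled in any case. The primary safety endpoint, the proportion completing at the maximal dose, is not affected.

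**What to change.** - **Synopsis, Statistical Methods:** limit the paired t-test sentence to the GDS, in line with section 3.7.2.2.
- **Sections 3.7.1.2 and 6.1.1:** for MDS-UPDRS Part III, report the number of subjects who worsen from Visit 1 by a threshold fixed in advance on the rigidity (3.3), bradykinesia (3.4 to 3.8 and 3.14), facial expression (3.2) and rest tremor (3.17 and 3.18) items, as n/N with an exact 95% CI.
- **Listing:** show each subject's item changes beside any parkinsonism reported as an adverse event.
- **Total score:** give it descriptively, without a p-value.
- **Additional display only:** results restricted to body regions free of dystonia at Visit 1. This should not be the main result, because generalized dystonia is eligible and may leave few such regions.

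The cost is small. The item scores are already on the form, so no new data are needed for the main count, but the additional display needs a rule linking items to body regions. The downside is that the threshold must be chosen and written down before analysis, and it must be stricter than any change on any one item. The intervals will be wide, which is an honest statement of what 15 subjects can show.

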3.2 Site

The AUDYT trial will be a single-center trial to be conducted at the University of Pennsylvania's Parkinson's Disease and Movement Disorders Center. This Center has ample experience in conducting clinical trials, and has the necessary infrastructure and qualified research staff to do so.

3.3 Number of Subjects

Given this is a pilot, single-center, open-label trial, a number of 15 study subjects was selected to guarantee recruitment (it is expected that 2 subjects will be recruited/month).

3.4 Study Population

Study subjects for the AUDYT trial will be subjects with dystonia being managed at the University of Pennsylvania, or referred to this center for the purpose of participation in the trial.

Subjects undergoing botulinum toxin injections for the treatment of dystonia will be eligible to participate in the study as long as they are willing to keep their upcoming injection paradigm identical to their latest injections, and as long as they are having suboptimal dystonia control with their current injection paradigm, as verified by their treating movement disorders specialist. Subjects receiving botulinum toxin injections will only be eligible to enroll in the AUDYT trial if their last injections were at least 11 weeks prior to screening (Visit 1). Subjects receiving injections sooner than every 12 weeks will be eligible to participate in the study as long as their upcoming injections are scheduled 6 days, or less, from the time of screening. It will be allowed for study subjects to undergo Visit 1 on the same day as their regularly-scheduled botulinum toxin injections, as long as Visit 1 (in its entirety) happens BEFORE the injections.

Subjects who have undergone Deep Brain Stimulation surgery for the treatment of dystonia will be eligible to participate in the study if their stimulation settings have remained unchanged for at least 3 months prior to study enrollment, and as long as they continue to have suboptimal dystonia control despite neurostimulation, as verified by their treating movement disorders specialist.

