3.4.1 Inclusion Criteria

- 1. Study subjects with definite dystonia (e.g. focal, segmental, multifocal and generalized), as established by a movement disorder specialist.
- 2. Study subjects of any race and either gender, age 18 or more on the date the informed consent form (ICF) is signed and with the capacity to provide voluntary informed consent.
- 3. Study subjects able to read and understand English and the ICF and are willing to comply with all study procedures, treatment and follow-up.

- 4. Study subjects who are taking any central nervous system acting medications (e.g., benzodiazepines, antidepressants, hypnotics), including medications for the treatment of dystonia, will be on a stable regimen for at least 30 days prior to the screening Visit, and will willing to remain on the same dose for the duration of the study.
- 5. Female of child-bearing potential will not be pregnant and will be using an acceptable method of contraception.
- 6. Study subjects with an MMSE >24.

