3.5.1.1 Visit 1: Screening (Week 1)

This will be the first study Visit. During this Visit, subjects will sign the informed consent form, their eligibility for study participation will be confirmed, and study drug will be dispensed. Demographic and baseline characteristics (age at screening, gender, weight, height, BMI, race, ethnicity, medical history, physical examination) will be listed for individual subjects. The activities to be performed during Visit 1 include:

- Informed consent
- Medical history will be obtained
- Medication history will be obtained. All prior medications will be assigned a generic name based on the World Health Organization (WHO) Dictionary.
- Concomitant medications will be reviewed (subjects receiving a strong CYP2D6 inhibitor will be
 instructed to titrate up to 36 mg during the ramp-up period, not to 48 mg, once study drug is
 dispensed). All concomitant medications will be assigned a generic name based on the World
 Health Organization (WHO) Dictionary. When applicable, date of last and next botulinum toxin
 injections will be recorded, as well as the date of the last DBS setting changes.
- Complete physical exam
- Vital signs
- 12-lead ECG
- C-SSRS
- SSS
- MMSE
- First video of the movement disorder examination

- MDS-UPDRS Part III
- Revision of eligibility criteria (inclusion/exclusion criteria will be reviewed)
- Dispense study drug (if eligible for participation)

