3.5.2.4 Dose Adjustment

Adjustments in the dose of AUSTEDO will be allowed throughout the study. If a reduction in the dose of AUSTEDO is required during the ramp-up period due to dose-limiting side effects, study subjects will be instructed to reduce the total daily AUSTEDO dose by 6 mg (1 tablet) every day until a new, maximum well-tolerated dose of AUSTEDO is established. A faster dose reduction will be allowed if deemed necessary by the investigator. Once this new dose is determined, the maintenance period will be considered initiated, and subjects will be instructed to complete Visit 3 and to remain on this dose for 6 weeks. Any side effects encountered will be recorded and reported as appropriate.

Dose-limiting toxicity will be defined in this protocol as the development of any of the following during the titration period: a) new or worsening depression, b) worsening of dystonic symptoms, c) QTc increase of >39 but <60 milliseconds from baseline, or d) any other sign or symptom that, at the PI's discretion, would preclude further safe titration of the study drug.

If a reduction in the dose of AUSTEDO is required during the maintenance period due to dose-limiting side effects, study subjects will be instructed to reduce the total daily AUSTEDO dose by 6 mg (1 tablet) every day until a new, maximum well-tolerated dose of AUSTEDO is established. A faster dose reduction will be allowed if deemed necessary by the investigator. Once this new dose is determined, subjects will be instructed to remain on this dose until the 6 weeks of the maintenance period are completed. A new maintenance period will NOT start every time a dose reduction is performed. Any side effects encountered will be recorded and reported as appropriate.

Increments in the total daily dose of AUSTEDO will not exceed 6 mg/week, as recommended by the package insert.³ Treatment interruptions will be discouraged unless necessary. In these cases, resuming AUSTEDO at the previous maintenance dose without titration will be allowed as long as the subject has been off study drug for 6 days or less. Subjects who require drug cessation for a week or more will be consider withdrawn from the trial, and will be asked to complete an early termination Visit.

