4.7 Prohibited Medications and Restrictions

Reserpine

Reserpine is an irreversible VMAT2 inhibitor, and, thus, will not be used concomitantly with AUSTEDO. In clinical practice, at least twenty (20) days must elapse after stopping reserpine before starting AUSTEDO.

Monoamine Oxidase Inhibitors

AUSTEDO is contraindicated in subjects taking MAOIs. In clinical practice, AUSTEDO will not be used in combination with an MAOI, or within 14 days of discontinuing therapy with an MAOI.

Tetrabenazine

AUSTEDO is contraindicated in subjects currently taking tetrabenazine. In clinical practice, AUSTEDO may be initiated the day following discontinuation of Tetrabenazine.

AUSTEDO is also contraindicated in subjects:

- Who are suicidal, or in subjects with untreated or inadequately treated depression.
- With hepatic impairment.
- 4.8 Concomitant Medications

Strong CYP2D6 inhibitors

As per the package insert,³ concomitant use of strong CYP2D6 inhibitors has been shown to increase the systemic exposure to the active dihydro-metabolites of AUSTEDO by approximately 3 fold. The daily dose of AUSTEDO will not exceed 36 mg per day, and the maximum single dose of AUSTEDO will not exceed 18 mg in subjects taking these inhibitors.

Table 5 below shows a list of strong CYP2D6 inhibitors:

Table 5 Strong CYP2D6 inhibitors
Bupropion
Fluoxetine
Paroxetine
Quinidine
Terbinafine

Neuroleptics

The risk for parkinsonism, NMS, and akathisia may be increased by concomitant use of AUSTEDO and dopamine antagonists or antipsychotics. As per the inclusion/exclusion criteria, subjects with a history of psychiatric disease or taking an antipsychotic (even if for a non-psychiatric reason) are not eligible for participation in the AUDYT trial.

Alcohol or other sedatives

Concomitant use of alcohol or other sedating drugs may have additive effects and worsen sedation and somnolence. As mentioned in the exclusion criteria, no change in the dose of psychoactive medications will be allowed for the duration of the trial, or at least 30 days prior to screening. Subjects will be encouraged to abstain from alcohol for the duration of the trial.

Drugs causing QTc prolongation

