6.1.2 Summary of Efficacy Data

The efficacy analysis population will include all enrolled subjects who receive at least one dose of study drug and who undergo both dystonia video examinations. Demographic data and key baseline characteristics will be summarized for the Efficacy population.

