11. APPENDICES

11.1 Appendix 1: Subject Visit schedule

	Screening	Dosing			Visit 5	Early termination
	Visit 1	Visit 2	Visit 3	Visit 4		Visit
Visit	Ramp-up starts		Maintanance starts	Maintanance ends	Post treatment	
Informed consent	X					
Eligibility Criteria	X					
Medical History	X					
Medication History	X					
Collect/review Adverse Events and Con Meds	X	X	X	X	X	X
Complete Physical Exam	X				X	X
Vital signs	X	X	X	X	X	X
12-lead ECG	X	X	X	X	X	X
CSSRS	X	X	X	X	X	X
Epworth Sleepiness Scale	X	X	X	X	X	X
MMSE	X			X		X
Video	X			X		X
MDS-UPDRS Part III	X			X		X
Patient Global Impression of Improvement				X		X
Dispense Study Drug (bottles)	X					
Collect returned bottles & assess compliance					X	X

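### DBS settings must be stable before enrolment, but nothing requires them to stay unchanged between the two efficacy assessments

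*Combined protocol and SAP*

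**What the plan says.** Section 3.4 (Study Population) sets two entry conditions for subjects who have had DBS surgery. One is that "their stimulation settings have remained unchanged for at least 3 months prior to study enrollment". The other is that their treating specialist confirms suboptimal control despite stimulation. Both look back from enrolment.

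Two other background treatments also carry a condition that looks forward. Subjects receiving botulinum toxin must be "willing to keep their upcoming injection paradigm identical to their latest injections" (3.4). Subjects on CNS-acting medicines, including those for dystonia, must be willing to "remain on the same dose for the duration of the study" (3.4.1, inclusion criterion 4). Section 4.8 restates this: "no change in the dose of psychoactive medications will be allowed for the duration of the trial".

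The only other mention of DBS settings is in the concomitant-medication item at Visit 1 (3.5.1.1), which records botulinum toxin dates "as well as the date of the last DBS setting changes". Appendix 1 schedules "Collect/review Adverse Events and Con Meds" at every visit without naming DBS. The efficacy population in 6.1.2 is every enrolled subject who takes at least one dose and "who undergo both dystonia video examinations".

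**The concern.** The trial has one arm. The PGI-I asks the subject at Visit 4 to compare now with the start of participation. The CGI-I compares the Visit 1 and Visit 4 videos, and the GDS is tested as a paired change between those visits (3.7.2.1 and 3.7.2.2). All three attribute change to the drug only so far as other treatment stays the same. The plan accepts this for toxin and CNS medicines, where it requires stability on study.

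A DBS adjustment between the two assessments is a change of active dystonia treatment. Blinding the raters to visit order guards against expectation but not against a real change produced by the stimulator. Because DBS subjects must have suboptimal control to enter, a wish to adjust settings during the study is plausible, although the documents give no rate. The distortion could go in either direction.

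**Working it through.** The plan gives no figure on this point, so the check is mainly a comparison of texts.

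**Step 1. Conditions side by side.**

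| Background treatment | Before entry | During the study |
|---|---|---|
| Botulinum toxin (3.4) | Last injections at least 11 weeks before screening; shorter cycles only if the next injection is within 6 days | Upcoming injections the same as the latest |
| CNS-acting medicines (3.4.1, 4.8) | Stable for at least 30 days before screening | Same dose throughout |
| DBS (3.4) | Settings unchanged for at least 3 months | No condition |

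**Step 2. Is the missing condition supplied elsewhere?** No rule on DBS settings during the study appears in 3.4.1 and 3.4.2 (eligibility), 3.5.2.4 (dose adjustment), 3.5.2.5 (withdrawal), 4.7 and 4.8 (prohibited and concomitant treatment), 6.1.2 (efficacy population), 6.2 (deviations) or Appendix 1. Inclusion criterion 3 asks for willingness to comply with study procedures, but fixed settings are not a stated procedure. Inclusion criterion 4 concerns medications and doses, which stimulation is not.

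**Step 3. What follows for a re-programmed subject.** The subject breaks no stated rule, has both videos, and stays in the efficacy population. No rule says how to treat that subject's data.

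**Step 4. Scale, as an illustration only.** Suppose k of 15 subjects were re-programmed and each one's GDS change moved by d, in units of the SD of the within-subject GDS change. Both k and d are assumptions; the documents give neither.

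- Shift in the mean change = k × d / 15.
- k = 1, d = 0.5: 1 × 0.5 / 15 = 0.033 SD.
- k = 2, d = 1: 2 × 1 / 15 = 0.133 SD.
- Half-width of the 95% interval at n = 15: t(0.975, 14) / √15 = 2.145 / 3.873 = 0.554 SD.

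Under these assumptions the shift, up or down, is 0.03 to 0.13 SD against a half-width of 0.55 SD. With k = 0 it is zero. The PGI-I and CGI-I are summarised by medians. With 15 subjects the median is the 8th ordered value, so one altered subject moves it by at most one rank and may not move it at all. The efficacy population may be smaller than 15, because withdrawn subjects are not replaced (3.5.2.5). Each remaining subject would then weigh somewhat more, and the interval would also be wider.

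**The case against.** The strongest reply is that the consequence is hypothetical twice over: no section says that any DBS subject is expected, or that any would be re-programmed. Entry already requires about 3 months of unchanged settings, and participation lasts at most 13 weeks (3.4.4), so the stable run-in is about as long as the study. The primary objective is safety and tolerability (2.1), and both the synopsis and 2.4 say the study is not powered for efficacy. All of this stands and limits the weight of the point. It does not supply the missing condition.

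A second reply is that the plan does not hold background treatment fully constant anyway. The toxin paradigm is fixed, but time since injection can differ between the two videos, because Visit 4 falls in week 12, week 10 or earlier depending on titration (3.5.1.4). That is fair. Closing the DBS gap would not make the comparison clean; it would remove one avoidable source of change.

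Three stronger readings are tempting and are not supported:

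- **That the tolerability endpoint is at risk.** A reader might reason that re-programming could produce "worsening of dystonic symptoms", which 3.5.2.4 lists as a dose-limiting toxicity. That chain is conjecture; nothing in the documents shows such an effect.
- **That a change would go unrecorded.** Concomitant medications are reviewed at every visit, and the Visit 1 item includes DBS dates. Later capture is therefore likely, though it has to be inferred because Appendix 1 does not name DBS.
- **That the damage could not be handled in analysis.** If the change is known, results can be shown with and without the subject. What cannot be recovered is that subject's own unconfounded Visit 4 assessment.

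**Conclusion.** The gap is real. Section 3.4 makes DBS stability a condition of entry only, while the plan requires on-study stability for botulinum toxin and CNS medicines. Re-programming between Visits 1 and 4 is permitted, and in an affected subject it would be confounded with drug effect in the PGI-I, CGI-I and GDS.

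The size is unknown and may be zero. It depends on how many DBS subjects enrol, how many are re-programmed and by how much their dystonia changes, none of which the documents give. The illustrative shifts rest on assumed values and are not evidence about this trial. A reader might infer that the efficacy results will be biased, but the documents support only that a bias is left open. Severity is low: this is a worthwhile tidy-up in an unpowered pilot.

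**What to change.** Add to the DBS paragraph in 3.4 that subjects must be willing to keep stimulation settings unchanged from Visit 1 through Visit 4, except where a change is needed for safety. Add to 6.1.2 that, if any subject's settings change in that interval for whatever reason, the PGI-I, CGI-I and GDS summaries will be reported with and without that subject.

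Optionally, say that the concomitant-medication review at each visit includes the date of any DBS setting change.

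The cost is one clause, one sentence, and a repeat summary only if a change occurs. No visit, procedure or sample size changes. The downside is that a few DBS candidates may decline; toxin candidates already accept a comparable condition.
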